5.3 Non-study drug antimalarials

Table 5-11 Table of non-study drug antimalarials with respective ATC codes

Non-study drug antimalarials	ATC code	ATC name
Aminoquinolines	P01BA01	Chloroquine
	P01BA02	Hydroxychloroquine
	P01BA03	Primaquine
	P01BA06	Amodiaquine
Biguanides	P01BB01	Proguanil
	P01BB02	Cycloguanil embonate
	P01BB51	Proguanil, combinations
Methanolquinoline	P01BC01	Quinine
	P01BC02	Mefloquine
Diaminopyrimidines	P01BD01	Pyrimethamine
	P01BD51	Pyrimethamine, combinations
Artemisinin and derivatives, plain	P01BE01	Artemisinin
	P01BE02	Artemether
	P01BE03	Artesunate
	P01BE04	Artemotil
	P01BE05	Artenimol
Artemisinin and derivatives, combinations	P01BF02	Artesunate and mefloquine
	P01BF03	Artesunate and amodiaquine
	P01BF04	Artesunate, sulphamethopyrazine and pyrimethamine
	P01BF05	Artenimol and piperazine
	P01BF06	Artesunate and pyronaridine
Other Antimalarials	P01BX01	Halofantrine
	P01BX02	Arterolane and Piperaquine

5.4 Medications for management severe malaria

Medications that are used for management of severe malaria will be identified from the clinical database before DBL.

5.5 AEs coding/grading

Adverse events are coded using the Medical dictionary for regulatory activities (MedDRA) terminology. AEs are assessed by investigators according to the most current Common Terminology Criteria for Adverse Events (CTCAE) version 5.0.

5.6 Laboratory parameters derivations

Grade categorization of lab values will be assigned programmatically as per NCI Common Terminology Criteria for Adverse Events (CTCAE) version 5.0 (specify version used in the RAP). The calculation of CTCAE grades will be based on the observed laboratory values only, clinical assessments will not be taken into account. The criteria to assign CTCAE grades are given in Novartis internal criteria for CTCAE grading of laboratory parameters. The latest available version of the document based on the underlying CTCAE version 5.0 at the time of analysis will be used.

A severity grade of 0 will be assigned for all non-missing lab values not graded as 1 or higher. Grade 5 will not be used. For laboratory tests that are graded for both low and high values, summaries will be done separately and labelled by direction, e.g., sodium will be summarized as hyponatremia and hypernatremia.

5.7 Computation of Blood Pressure Percentiles for Arbitrary Sex, Age, and Height

Below algorithm is described in the Appendix B of the following reference: The Fourth Report on Diagnosis, Evaluation and Treatment of High Blood Pressure in Children and Adolescents. Pediatrics 2004; 114; 555.

- To compute the systolic blood pressure (SBP) percentile of a boy whose age is y years and height = h inches with $SBP = x$ mmHg:
 - Convert the height of h inches to a height Z-score relative to boys of the same age (as per data tables provided [Table 5-14](#); this is denoted by Z_{ht} . For age < 2 years, age is recorded in the CRF with month as the unit and will be converted into year with 1 decimal, the corresponding height Z score can be calculated using months (See [Table 5-13](#)).
 - Compute the expected SBP (μ) for boys of age y years and height h inches given by

$$\mu = \alpha + \sum_{j=1}^4 \beta_j (y - 10)^j + \sum_{k=1}^4 \gamma_k (Z_{ht})^k$$

where, regression coefficients are given in the 3rd column of [Table 5-12](#)

- Then convert the boy's observed SBP (x) to a Z-score (Z_{BP}) given by

$$Z_{BP} = \frac{(x - \mu)}{\sigma}$$

where, σ is given in the 3rd column for standard deviation row of [Table 5-12](#)

- To convert the bp Z-score to a percentile (P), compute $P = \Phi(Z_{BP}) \times 100\%$
where $\Phi(Z)$ = area under a standard normal distribution to the left of Z.

- Likewise, to compute percentiles for SBP for girls, diastolic blood pressure (DBP) (K5) for boys, and DBP (K5) for girls, use the regression coefficients from the 4th, 5th, and 6th columns of [Table 5-12](#).

For example, a 12-year-old boy, with height at the 90th percentile for his age-sex group, has a height Z-score = 1.28, and his expected SBP (μ) is

$$\mu = 102.19768 + 1.82416 (2) + 0.12776 (2^2) + 0.00249 (2^3) - 0.00135 (2^4) + 2.73157 (1.28) - 0.19618 (1.28^2) - 0.04659 (1.28^3) + 0.00947 (1.28^4) = 109.46 \text{ mmHg.}$$

Table 5-12 Regression coefficients from Blood Pressure Regression Models

Regression Coefficients From Blood Pressure Regression Models*					
Variable Name	Symbol	Systolic BP		Diastolic BP5	
		Male	Female	Male	Female
Intercept	α	102.19768	102.01027	61.01217	60.50510
Age					
Age-10	β_1	1.82416	1.94397	0.68314	1.01301
(Age-10) ²	β_2	0.12776	0.00598	-0.09835	0.01157
(Age-10) ³	β_3	0.00249	-0.00789	0.01711	0.00424
(Age-10) ⁴	β_4	-0.00135	-0.00059	0.00045	-0.00137
Normalized height					
Zht	γ^1	2.73157	2.03526	1.46993	1.16641
Zht ²	γ^2	-0.19618	0.02534	-0.07849	0.12795
Zht ³	γ^3	-0.04659	-0.01884	-0.03144	-0.03869
Zht ⁴	γ^4	0.00947	0.00121	0.00967	-0.00079
Standard deviation	σ	10.7128	10.4855	11.6032	10.9573
ρ^\dagger		0.4100	0.3824	0.2436	0.2598
n (persons)		32,161	31,066	24,057	23,443
n (visits)		42,074	41,017	29,182	28,794

BP, blood pressure; Diastolic BP5, diastolic measurement at Korotkoff 5.

* The coefficients were obtained from mixed-effects linear regression models.

† The value of ρ represents the correlation between BP measurements at different ages for the same child after correcting for age and Zht. This computation was necessary because some studies contributing to the childhood BP database provided BP at more than one age.

Computation of Z-score for height:

As per the recommendation from Centers for Disease Control and Prevention (CDC) use WHO growth charts for 0 to < 2 years of age and CDC growth charts for age ≥2 years. Accordingly, convert the given height into corresponding Z-score as per [Table 5-13](#) and [Table 5-14](#) given for the growth standards using the following formula.

$$Z_{ht} = \frac{\left(\frac{\text{height}}{\text{median}}\right)^L - 1}{L * S}$$

Where, median, L, S (i.e. CV) are provided in the [Table 5-13](#) for age up to 2 years and in [Table 5-14](#) for age 2-20 years; height in centimeters.

Table 5-13 **Table for WHO standard Length-for-age growth chart for age 0 to to 2 years**

Month	L	Boy		Girl	
		Median (cm)	S (CV)	Median (cm)	S (CV)
0	1	49.8842	0.03795	49.1477	0.0379
1	1	54.7244	0.03557	53.6872	0.0364
2	1	58.4249	0.03424	57.0673	0.03568
3	1	61.4292	0.03328	59.8029	0.0352
4	1	63.886	0.03257	62.0899	0.03486
5	1	65.9026	0.03204	64.0301	0.03463
6	1	67.6236	0.03165	65.7311	0.03448
7	1	69.1645	0.03139	67.2873	0.03441
8	1	70.5994	0.03124	68.7498	0.0344
9	1	71.9687	0.03117	70.1435	0.03444
10	1	73.2812	0.03118	71.4818	0.03452
11	1	74.5388	0.03125	72.771	0.03464
12	1	75.7488	0.03137	74.015	0.03479
13	1	76.9186	0.03154	75.2176	0.03496
14	1	78.0497	0.03174	76.3817	0.03514
15	1	79.1458	0.03197	77.5099	0.03534
16	1	80.2113	0.03222	78.6055	0.03555
17	1	81.2487	0.0325	79.671	0.03576
18	1	82.2587	0.03279	80.7079	0.03598
19	1	83.2418	0.0331	81.7182	0.0362
20	1	84.1996	0.03342	82.7036	0.03643
21	1	85.1348	0.03376	83.6654	0.03666
22	1	86.0477	0.0341	84.604	0.03688
23	1	86.941	0.03445	85.5202	0.03711

Reference:

https://www.cdc.gov/growthcharts/who/boys_length_weight.htm

https://www.cdc.gov/growthcharts/who/girls_length_weight.htm

Table 5-14 Table for CDC growth standard height-for-age growth charts for age 2-20 years

Age(year)	Boy			Girl		
	L	Median (cm)	S (CV)	L	Median (cm)	S (CV)
2	0.941524	86.4522	0.040322	1.072449	84.97556	0.040791
3	-0.39092	95.27359	0.040534	0.541981	94.21336	0.042018
4	0.827637	102.5105	0.041344	0.225706	101.0339	0.04326
5	1.266367	109.1751	0.042593	-0.05773	107.9566	0.044277
6	1.137443	115.6609	0.043673	-0.21907	115.0055	0.044964
7	0.753244	122.0305	0.044403	-0.21021	121.7617	0.045461
8	0.455268	128.1237	0.045127	-0.07928	127.8263	0.045968
9	0.415687	133.7345	0.046217	0.084148	133.1304	0.046884
10	0.505564	138.8234	0.04761	0.284749	138.2112	0.048705
11	0.487939	143.7304	0.048938	0.74429	144.2609	0.050524
12	0.420919	149.3088	0.049948	1.303045	151.4866	0.048599
13	0.81624	156.4099	0.050333	1.242968	157.3437	0.043859
14	1.670433	164.1418	0.048945	0.956572	160.4777	0.041022
15	2.20518	170.1393	0.04589	0.89557	161.898	0.040084
16	2.113023	173.6101	0.043086	0.941146	162.569	0.039821
17	1.724738	175.341	0.041408	0.999506	162.9238	0.039732
18	1.399999	176.185	0.040644	1.047571	163.1308	0.039687
19	1.229163	176.6179	0.040391	1.083315	163.259	0.039657
20	1.167279	176.8492	0.04037	1.108046	163.3383	0.039636

Reference: <https://www.cdc.gov/growthcharts/data/zscore/statage.csv>

5.8 Statistical models

5.8.1 Primary analysis

The primary analysis of parasite clearance rate $\geq 90\%$ reduction at 12 hours is defined in [Section 2](#). The between treatment difference will be evaluated using a Wilson uncorrected method using PROC FREQ with RISKDIFF (CL= NEWCOMBE) option in the TABLES statement.

5.8.2 Key secondary analysis

The key secondary analysis of clinical success at 48 hours is defined in [Section 2](#).

SAS procedure FREQ with EXACT statement for one-way tables will be used to estimate the proportion of responders (binary outcome = 1 or “Yes”), along with the associated 95% (=100 \times (1 – two-sided α level)) two-sided Clopper- Pearson CI.

Between treatment difference will be evaluated using a Mantel-Haenszel estimate of the treatment difference in responder rates stratified by cohort (Cohorts 1 and 2 pooled) using PROC FREQ with RISKDIFF(COMMON) option in the TABLES statement.

Clinical success at other timepoints will be analyzed similarly.

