8.3.1 Clinical outcome in moderately severe and severe malaria

8.3.1.1 Clinical success

Clinical success in study participants will be evaluated at various time points throughout the study. Clinical success at 48 hours is considered as a key secondary endpoint. Clinical success is a composite endpoint based on the criteria shown below ([Table 8-3](#)).

Table 8-3 Definition of clinical success in the study at any time point

Disease criteria	Clinical failure (participant meeting any of the criteria)	Clinical success (participant has to meet all criteria)
Dead or Alive	Dead [#]	Alive
Presence of asexual parasites	Yes	No
Presence of any of the key signs of severe malaria*	Yes	No

[#] Death - All in hospital deaths and malaria related deaths (as per adjudication committee) occurring after hospital discharge
 
* Key signs of Severe Malaria defined as
 
1) Altered consciousness (including prostration) – Prostration (inability to sit or drink or breast feed) or Glasgow Coma Score < 11 (in participants > 5 years of age) or a Blantyre coma score of < 3 in children (≤ 5 years)
 
2) Renal impairment – SCr ≥ 3x ULN or Absolute SCr >3mg/dL or use of Renal Replacement Therapy (RRT)
 
3) Acidosis – Plasma lactate > 4 mmol/L or Respiratory distress defined as rapid, deep and labored breathing (costal indrawing, use of accessory muscles and nasal flaring).
		

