Intercurrent events and other non-intercurrent events including partial missing data that may occur and affect the derivation of secondary estimand will be handled in [Section 12.2](#). Note: partial data missing should be rare since participants are still hospitalized at 48 hours.

Table 12-2 Handling of intercurrent events and other events that may occur and affect the derivation of secondary estimand

Event	Outcome
Receive IV antimalarial rescue medication prior to 48 hours	Not clinical success
Discontinue the study prior to 48 hours, such as withdrawal of consent, COVID-19, etc.	Not clinical success due to early discharge
Missing parasite assessment at 48 hours ^{\$}	
 • Not clinical success if asexual parasites present in the latest visit prior to 48 hours • Ignored* otherwise
Altered consciousness: missing Prostration, missing Glasgow Coma Score or missing Blantyre coma score in relevant age groups ^{\$}	Use the result from the latest visit prior to 48 hours (including baseline) for each missing item
Renal impairment: missing SCr ^{\$}	
 • Not clinical success if Renal Replacement Therapy is used at 48 hours • Use the latest SCr prior to 48 hours
Acidosis and respiratory distress: missing plasma lactate or missing respiratory distress assessment ^{\$}	Use the result from the latest visit prior to 48 hours (including baseline) for each missing item
* determination of clinical success depends on other assessments.	
^{\$} Partial data missing, unlikely since participants are in the hospital	

Two-sided 90% confidence intervals (CI) for the proportion of participants with clinical success at 48 hours will be provided based on the exact method (Clopper-Pearson method). In addition, 2-sided 90% CIs for the difference between a cipargamin dose regimen and artesunate will be provided using a Mantel-Haenszel estimate of the common risk difference stratified by cohort where Cohorts 1 and 2 will be combined. Mantel-Haenszel estimate is a weighted risk difference with weight roughly proportional to strata size. It's an unbiased estimation of risk difference in the population under the following assumptions either (1) the risk difference is

same across different strata or (2) the strata sizes in study resemble the strata size in the disease population at large.

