- For **height in cm** and **SCr in mg/dL**: $\text{eGFR (ml/min/1.73 m}^2\text{)} = 0.413 \times (\text{height/SCr})$
- For **height in cm** and **SCr in $\mu\text{mol/L}$** : $\text{eGFR (ml/min/1.73 m}^2\text{)} = 36.5 \times (\text{height/SCr})$

Normal renal GFR values, as measured by inulin clearance ([Schwartz and Furth 2007](#)), are provided in [Table 16-4](#) below:

Table 16-4 **Normal GFR in children and young adults, as assessed by inulin clearance (adapted for pediatric participants included in this study)**

Age	Mean GFR \pm SD (ml/min per 1.73 m ²)
Term babies	
4-6 months	87.4 \pm 22.3
7-12 months	96.2 \pm 12.2
1-2 years	105.2 \pm 17.3
Children	
3-4 years	111.2 \pm 18.5
5-6 years	114.1 \pm 18.6
7-8 years	111.3 \pm 18.3
9-10 years	110.0 \pm 21.6
11-12 years	116.4 \pm 18.9
13-15 years	117.2 \pm 16.1
2.7-11.6 years	127.1 \pm 13.5
9-12 years	116.6 \pm 18.1
Young adults	
16.2-34 years	112 \pm 13

16.3

CCI

Table 16-5

CCI

CCI

16.4 Appendix 4: Modified version of WHO classification of signs of severe *P. falciparum* malaria

Severe malaria is defined as occurrence of one or more of the following observations, in the absence of an identified alternative cause, and in the presence of *P. falciparum* asexual parasitemia (WHO 2014)

Table 16-6 Definition of severe malaria

Signs	Definition
Impaired consciousness	A Glasgow Coma Score < 11 in adults or a Blantyre coma score < 3 in children
Prostration	Generalized weakness so that the person is unable to sit, stand or walk without assistance
Multiple convulsions	More than two episodes within 24 hours
Acidosis*	venous plasma lactate ≥ 4 mmol. Severe acidosis manifests clinically as respiratory distress – rapid, deep and laboured breathing
Hypoglycaemia	Blood or plasma glucose < 2.2 mmol (< 40 mg/dL)
Severe malarial anaemia	A haemoglobin concentration < 5 g/dl or a haematocrit of < 15% in children < 12 years of age (< 7 g/dl or < 20%, respectively, in adults) together with a parasite count > 10,000/ μ l
Renal impairment (acute kidney injury)**	Plasma or serum creatinine > 265 μ mol/L (3 mg/dL) or ≥ 3 x ULN or blood urea > 20 mmol/L
Jaundice	Plasma or serum bilirubin > 50 μ mol/L (3 mg/dL) with a parasite count > 100,000/ μ l
Pulmonary edema	Radiologically confirmed, or oxygen saturation < 92% on room air with a respiratory rate > 30/min, often with chest indrawing and crepitations on auscultation

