Key signs of Severe Malaria are Altered consciousness, Renal impairment, Acidosis, and Respiratory distress.

Signs of severe malaria

The following signs of severe malaria will be monitored at every visit during the entire study duration.

- **Altered consciousness** – Prostration (inability to sit or drink or breast feed) or GCS < 11 for patients > 5 years / BCS < 3 for patients ≤ 5 years of age
- **Renal Impairment** - Serum creatinine > 3xULN or > 3 mg/dL or need for renal replacement therapy (RRT)
- **Acidosis** - Plasma lactate > 4 mmol/L or Respiratory distress.
Respiratory distress is defined as rapid, deep and labored breathing (costal indrawing, use of accessory muscles and nasal flaring)- present or absent.
In database, Plasma lactate is captured under lactic acid.
- **Severe anemia** - Hb < 5 g/dl or Hb < 7g/dl in pediatric and adults respectively or need of blood transfusion
- **Jaundice** - Serum bilirubin > 3 mg/dl
- **Hypoglycemia**- plasma glucose < 40 mg/dL
- **Blantyre coma scale (BCS)** is a number from 0 to 5 based on [Appendix 5, Table 5-1](#) for patients ≤ 5 years. The score is determined by adding the results from three categories: Motor response, verbal response, and eye movement. The minimum score is 0 which indicates poor results while the maximum is 5 indicating good results.

- **Glasgow Coma Scale (GCS)** is a clinical scale used to reliably measure a person's level of consciousness for age > 5 years. The score is determined by adding the results from three categories: Motor response, verbal response, and eye movement. A person's GCS score can range from 3 (completely unresponsive) to 15 (responsive) based on [Appendix 5, Table 5-2](#).

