2.6 Analysis of the key secondary objective

2.6.1 Secondary estimand

The secondary clinical question of interest is: What is the difference between IV cipargamin and IV artesunate in clinical success at 48 hours without the need of IV rescue antimalarial medication?

The justification for the secondary estimand is that it will reflect the clinical outcome including recovery from the most severe symptoms of the disease with IV treatment before earliest possible administration of oral antimalarial medication at 48 hours. This objective is being evaluated for possible use in Phase III study.

The secondary estimand is described by the following attributes:

1. **Population:** patients with severe *P. falciparum* malaria and treated with at least one dose of IV study medication. Further details about the population are provided in Section 5 in the protocol.
2. **Variable:** A binary outcome indicating clinical success- patient is alive and has absence of asexual parasites and no critical signs of severe malaria (See [Section 2.1.1](#) for further details) at 48 hours.
3. **Treatment of interest:** IV cipargamin vs IV artesunate. Further details about cipargamin and artesunate are provided in Section 6 in the protocol.
4. **Intercurrent event:** receive IV rescue antimalarial medication before assessing the clinical success prior to H48.
5. **Summary measure:** Proportion of patients with clinical success with 90% CI within a treatment group as well as the difference between the cipargamin and artesunate treatment group.

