2.6.6 Supportive analysis for secondary estimand

Clinical success at 48 hours will be summarized descriptively by the subgroups defined in [Section 2.2.1](#).

The analyses specified in [Section 2.6.2](#) and [Section 2.6.5](#), will be repeated using the PPS. Additionally, analysis specified in Section 2.6.2 may be performed using the PPS after excluding the patients who took other antimalarial drugs (PD ID= COMD01) before assessing the clinical success at 48 hours, if in case there are enough number of such patients exists.

A 2-sided 90% CIs for the proportion of patients with clinical success for each treatment group will be provided based on the Clopper-Pearson exact method on pooled cohorts.

A 2-sided 90% CIs for treatment difference between cipargamin and artesunate will be provided by cohort using the Wilson uncorrected method.

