Altered consciousness – Prostration (inability to sit or drink or breast feed) or GCS < 11 for patients > 5 years / BCS < 3 for patients ≤ 5 years of age. Prostration, GCS/ BCS is recorded by investigator in the relevant CRF. In case that a patient completes the visit but the data are missing, this will be determined to be ‘yes’ if a patient has an AE of “Altered state of consciousness” with starting day since previous visit to the current visit and ‘no’ otherwise.

Renal Impairment - Serum creatinine > 3xULN or > 3 mg/dL or need for renal replacement therapy (RRT). Serum creatinine is recorded in the point of care devices (POC) or using local lab in case of non-availability of POC and renal replacement is recorded by investigator in the concomitant CRF. In case that a patient completes the visit but the serum creatinine is missing, this will be determined to be ‘yes’ if a patient has an “renal replacement” concomitant with starting day since previous visit to the current visit and ‘no’ otherwise.

Acidosis - Plasma lactate ≥ 4 mmol/L (In database, lactate is captured under lactic acid) or Respiratory distress. Plasma lactate is recorded in the point of care devices (POC) or using local lab in case of non-availability of POC and respiratory distress is recorded by investigator in the severe malaria CRF. In case that a patient completes the visit but the data are missing, this will be determined to be ‘yes’ if a patient has an AE of “Respiratory distress” with starting day since previous visit to the current visit and ‘no’ otherwise.

Single imputation rule:

Following single imputations will be performed before applying the multiple imputations:

After a patient has parasite clearance, any intermediate missing parasite between 2 negative parasite assessments is imputed as negative parasite assessment since it is very likely that the intermediate missing should also be negative as prior and post missing data show negative result.

Once a patient died before hospital discharge or is declared as malaria related death at a timepoint, the patient will be considered as not achieving the clinical success for the timepoint onwards.

If a patient has parasite reappearance after the hospital discharge, the patient is considered as not achieving the clinical success for the timepoint onwards.

If a patient receives IV antimalarial rescue medication prior to hospital discharge, the patient is considered as not achieving the clinical success for the timepoint onwards.

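### SAP 5.8.2 sets a 95% interval for single-arm clinical success where the rest of the plan uses 90%, and the endpoint's lactate and creatinine cut-offs do not agree between sections

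*SAP*

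**What the plan says.** **Interval level.** SAP 5.8.2 describes the SAS procedure for the single-arm clinical success proportion at 48 hours and gives the estimate "along with the associated 95" per cent two-sided Clopper-Pearson interval, glossed as 100 x (1 - two-sided alpha). It adds that clinical success at other timepoints will be analyzed in a similar way. The other sections say 90%:

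- Protocol 12.5.1: "Two-sided 90% confidence intervals (CI) for the proportion of participants with clinical success" at 48 hours, by the exact method.
- SAP 2.6.1, summary measure: "Proportion of patients with clinical success with 90% CI within a treatment group".
- SAP 2.6.6: "A 2-sided 90% CIs for the proportion of patients with clinical success for each treatment group", by Clopper-Pearson on pooled cohorts.
- SAP 2.7.2.1: 90% Clopper-Pearson intervals at the other timepoints.
- Protocol 12.8.2 and SAP 3.2: every precision figure is for a 90% interval.

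For the between-treatment difference, SAP 2.6.2 specifies a 90% Mantel-Haenszel interval. The procedure descriptions in 5.8.1 (primary difference) and 5.8.2 (clinical success difference) name no level. SAP Section 4 reports no change to protocol-specified analyses.

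**Cut-offs.** SAP 2.1.1 defines acidosis as "Plasma lactate > 4 mmol/L or Respiratory distress", as does protocol Table 8-3. SAP 5.8.4 says it restates 2.1.1 but gives "Plasma lactate ≥ 4 mmol/L". For creatinine, Table 8-3 includes a value equal to 3 x ULN; protocol 8.3.1.2 and SAP 2.1.1 and 5.8.4 require a value above it.

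**Prostration.** The outcome definition (Table 8-3, SAP 2.1.1, SAP 5.8.4) is "Prostration (inability to sit or drink or breast feed". The entry definition in protocol Table 16-6 is "Generalized weakness so that the person is unable to sit, stand or walk without assistance".

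**The concern.** SAP 5.8.2 is where the analysis of the key secondary endpoint is turned into procedure calls, and the only confidence level it gives disagrees with the sections it implements. Because it extends the same treatment to other timepoints, the discrepancy covers the whole series of single-arm clinical success intervals. Where the calls for differences give no level, nothing in the programming section corrects the impression that alpha is 0.05.

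The operator mismatches mean that one patient, with one set of data, could be a success under one section and a failure under another. For lactate, the multiple-imputation sensitivity analysis would use a slightly different endpoint from the analysis it is meant to check. For creatinine, the protocol itself gives two answers: the secondary estimand (protocol 2.2) points to 8.3.1.2 for the signs, while 12.5.1 points to Table 8-3.

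The composite is being used for the first time and may become the Phase III primary endpoint, so its rate, interval and exact definition are outputs this trial has to deliver cleanly.

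**Working it through.** **Inputs** (protocol 12.8.2, SAP 3.2): assumed success 0.75 in both arms; target half-width 0.1 with at least 80% probability; 107 evaluable per arm; about 8% excluded from the FAS.

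**Step 1. Reproduce the plan's figures.** By exact binomial enumeration, find the smallest n with Pr(half-width ≤ 0.1) ≥ 0.80. The single-arm interval is Clopper-Pearson: lower limit = Beta quantile at α/2 with parameters (x, n − x + 1); upper limit = Beta quantile at 1 − α/2 with parameters (x + 1, n − x). The interval for the difference is Wilson uncorrected (Newcombe).

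| Quantity | Plan | 90% interval | 95% interval |
|---|---|---|---|
| Single arm, p = 0.5 | 76 | 76 | 104 |
| Single arm, p = 0.7 | 70 | 70 | 94 |
| Difference, p = 0.5 | 133 | 133 | 189 |
| Difference, p = 0.75 | 107 | 107 (probability 0.838) | 150 |

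All four planned figures match exactly at 90% and none matches at 95%. The randomized number also agrees: 107 / 0.92 = 116.3, against about 116 stated, and 6 + 14 + 38 + 38 + 20 = 116.

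**Step 2. Effect of 95% on the single-arm interval.** 107 x 0.75 = 80.25, so take x = 80.

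- 90%: 0.669 to 0.816, half-width 0.073.
- 95%: 0.654 to 0.827, half-width 0.086.
- Ratio: 0.0861 / 0.0732 = 1.18, so about 18% wider.

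At p = 0.75 a single arm needs 65 for the 0.1 target at 90% and 87 at 95%. Both are below 107, so the target is still met at either level.

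**Step 3. What if 95% were carried over to the difference?** The SAP does not say this. If it happened, n = 107 would reach a half-width of 0.1 or less with probability 0.001 instead of 0.838. This is the reason to state alpha in the calls; it is not a forecast of what will be done.

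**Step 4. Cut-offs side by side.**

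| Sign | Table 8-3 | Protocol 8.3.1.2 | SAP 2.1.1 | SAP 5.8.4 |
|---|---|---|---|---|
| Lactate (mmol/L) | > 4 | > 4 | > 4 | ≥ 4 |
| Creatinine (x ULN) | ≥ 3 | > 3 | > 3 | > 3 |

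A patient's classification changes only if lactate is exactly 4 mmol/L, or creatinine exactly 3 x ULN with no other criterion met. The documents give no distribution from which to estimate how often that occurs.

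**The case against.** The strongest reply is that these are editorial slips whose answer is already in the plan. SAP 5.8.2 opens by referring to Section 2 for the definition of the analysis, and Section 2 says 90%. The 95% reads like leftover template text. The ≥ 4 lactate rule sits in a sensitivity section that says it restates 2.1.1 and later derives success from 2.1.1 in each completed dataset. This stands as far as intent goes: 90% is clearly what was meant. It does not remove the need for a correction, because 5.8.2 states an operative figure and a careful programmer could follow either section.

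Four stronger readings are tempting, and the documents do not support them.

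- *The reported interval is not the one the trial was sized for.* Sizing was on the 90% interval for the difference. SAP 5.8.2 gives no other level for that difference, and 2.6.2 keeps it at 90%. The single-arm interval did not determine n.
- *A clinical success at 48 hours can still meet the entry definition of severe malaria.* Table 8-3 requires absence of asexual parasites, and protocol 16.4 requires their presence. On observed data nobody can satisfy both; only a missing 48-hour smear leaves a gap.
- *One CRF box serves both prostration definitions.* The CRF is not among the documents. Table 8-4 lists a Yes/No prostration item, but the assessment schedules have a separate severe-malaria examination row tied to Table 16-6, and SAP 5.8.4 names a severe malaria CRF.
- *All three signs conflict within the SAP.* Only lactate does. Creatinine and prostration are worded the same in 2.1.1 and 5.8.4.

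**Conclusion.** The point holds as a specification error with a small numerical effect. The 95% level in SAP 5.8.2 contradicts the protocol, the SAP's own estimand and analysis sections, and the precision calculation. It would widen the single-arm interval from a half-width of 0.073 to 0.086, assuming 107 evaluable patients and about 75% success as the plan does. The precision target would still be met and the sample size is unaffected. The interval for the difference is correctly specified in SAP 2.6.2; what is missing is a stated level in the procedure calls.

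The lactate and creatinine operators conflict, with consequences only at exact threshold values; their frequency is unknown.

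The prostration texts differ between entry and outcome, but the outcome text is consistent wherever it appears, so this is not a conflict within the endpoint. Entry and outcome definitions may legitimately differ; the documents give no reason for this difference and should either reconcile the passages or explain it.

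**What to change.** - In SAP 5.8.2, change 95% to 90%, which also settles the other timepoints.
- State alpha = 0.10 in the procedure calls in SAP 5.8.1 and 5.8.2, including the Mantel-Haenszel difference.
- Reconcile the lactate and creatinine operators across protocol Table 8-3, protocol 8.3.1.2, SAP 2.1.1 and SAP 5.8.4, so that each sign has one rule.
- Reconcile the prostration wording in Table 16-6 with that in Table 8-3 and SAP 2.1.1, or add a sentence explaining why entry and outcome differ.

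The cost is a SAP wording revision and a short protocol clarification. No change to design, sample size or data collection is needed for the interval level or the operators.
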